# 13.9.7. Pooling

Subgroup analysis of the primary efficacy endpoint by center will be used to evaluate the poolability of the results. The subject continuous quit status at week 6 by center interaction will be tested with a logistic regression model, using a significance level of 10%. If the interaction is found significant, the reasons for these interactions will be further explored and rationalized. This evaluation may include demographic features, symptoms at presentation, clinical and treatment history, and center comparability in the features found to be associated with the primary efficacy variable. Sites with a small amount of subjects (<10) will be pooled together for this analysis by geographical location.

# 13.9.8. Handling of missing data

If a subject missed a clinic visit but had been abstinent (i.e., a negative confirmatory test) at the clinical visits prior to and following the missing visit, and claimed abstinence throughout, that subject will be classified as abstinent. Dropouts and subjects lost to follow will be classified as non-abstinent.

Additionally, the following methods of imputation may be used for the primary endpoint as further sensitivity analyses:

- Tolerability/Imputation: Assume all subjects terminated from the study due to tolerability issues are failures. For other subjects, the outcome will be obtained from the last valid assessment.
- Last Observation Carried Forward: Most recent visit with a valid assessment will be carried forward and used for the endpoint determination for these subjects.
- Multiple Imputation: Impute endpoint data using a multiple imputation model based on sex, age, race and history of smoking at baseline, as well as endpoint data computed at each intermediate time-point for all subjects with observed data.
- Best Case Scenario: Assume all subjects with missing data in the active group are successes; Assume all subjects in the sham group with missing data are failures.
- Worst Case Scenario: Assume all subjects with missing data in the active group are failures; Assume all subjects in the sham group with missing data are successes.

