### 13.2. Study Endpoints

# 13.2.1. Primary Efficacy Endpoint

The primary endpoint is the four-week continuous quit rate (CQR), representing abstinence during a consecutive 4 week period. Weekly abstinence is defined as a subject's self-report (in diary) of no smoking (0 cigarettes/day during the whole week), confirmed by urine cotinine levels  $\leq 200$  ng/ml. A missing confirmatory test will be considered negative, if the previous and the following weekly or 4 month follow-up confirmatory tests are negative. Quit rates are defined as the ratio of the number of patients meeting the quit criterion for at least 4 consecutive weeks to the number of patients initially treated and having at least one post-baseline assessment.

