### 13.4. Sample size

The preliminary clinical study evaluated the safety and efficacy of the DTMS as an aid in smoking cessation, at three weeks and at six months follow-up. The three week point prevalence quit rate was 44% in the treatment group and 13% in the sham group. The six month point prevalence quit rate was 33% in the treatment group and 9% in the sham group. Although, the three week point prevalence quit rate showed a significant improvement in the treatment group compared to the sham group, the point prevalence quit rate did not meet the standard requirement for evaluating smoking cessation, i.e., at least a 4 week continuous quit rate. Furthermore, the six month data had its limitations, including a long term time point and high drop-out rate. Therefore, we looked at the clinical results provided in support of FDA approval of other smoking cessation aids, including Zyban (Bupropion hydrochloride) and Chantix (Varenicline). The mechanism of action of Zyban which aids smoking cessation is the increase in dopamine release, which is also one of the mechanisms of action of the DTMS treatment.

The quit rates (i.e., based on abstinence from week 4 of the study through week 7) were 49% in the treatment group receiving Zyban compared to 36% in patients receiving Nicotine Replacement Therapy (NRT) and 23% in the placebo group. In two other studies, subjects treated with Chantix had an abstinence rate during weeks 9 through 12 of 44% compared to 30% in patients treated with Zyban and 17% and 18% in patients receiving placebo.

For the purpose of sample size calculation the weighted average of the quit rates for smoking cessation treatments (including Zyban, Chantix, NRT and DTMS) (38.6%) and the weighted average of the quit rates for placebo/sham (18.4%) will be used. Using the above weighted averages we can assume a placebo/sham success rate of 18%, and a minimally important difference of 20%.

The study is designed to have 80% power with a two-sided level of significance of 5% to detect to detect a difference of 20% in the CQR in the DTMS group compared to the control group, and one planned interim analyses using the Lan De-Mets alpha spending approach with a Pocock type spending function (the calculations were performed using the SAS SEQDESIGN procedure).

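### Two optional sensitivity analyses (LOCF and the tolerability rule) let the last visit decide a four-week continuous endpoint, so a drop-out with fewer than four observed abstinent weeks can be scored as a four-week quitter

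*Protocol*

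**What the plan says.** Section 13.2.1 defines the primary endpoint: "The primary endpoint is the four-week continuous quit rate (CQR), representing abstinence during a consecutive 4 week period". Each week needs a diary with no cigarettes and a confirming cotinine result, and the numerator is the number of "patients meeting the quit criterion for at least 4 consecutive weeks".

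Section 13.9.8 sets the main missing-data rule. A missed visit between two negative ones is bridged; otherwise, "Dropouts and subjects lost to follow will be classified as non-abstinent".

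The same section then says that "the following methods of imputation may be used for the primary endpoint as further sensitivity analyses". Five methods follow, and two concern this point:

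- Last observation carried forward (LOCF): "Most recent visit with a valid assessment will be carried forward and used for the endpoint determination for these subjects".
- Tolerability: "Assume all subjects terminated from the study due to tolerability issues are failures". The rule continues: "For other subjects, the outcome will be obtained from the last valid assessment".

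The other three are multiple imputation, a best case and a worst case. Section 11.1.4 places the weekly assessments at weeks 2 to 6 and the target quit date 7 to 14 days after the first session.

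**The concern.** A weekly assessment gives a one-week status, while the endpoint needs four such weeks in a row. Both rules settle the endpoint from the last visit and set no minimum number of observed abstinent weeks. A subject who is abstinent at week 3 and then leaves is a failure under the main rule. LOCF fills weeks 4 to 6 with abstinence and makes the same subject a four-week quitter.

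For such subjects the analysis reports abstinence at the last visit. In choosing its planning effect, section 13.4 sets aside the pilot's result on that kind of measure because "the point prevalence quit rate did not meet the standard requirement for evaluating smoking cessation". Both rules also assume that nobody relapses after leaving. Section 2.1 reports that more than 85% of smokers who try to quit on their own relapse, most of them within a week. That figure is for unaided attempts, so it shows only that the assumption is a strong one.

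At stake is the meaning of a result that would be reported as showing the four-week continuous quit rate (CQR) to be robust.

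**Working it through.** **The plan's own figure.** The plan gives no figure for the effect of these rules. Its sample size reproduces and does not use them. With 18% vs 38%, 80% power and two-sided 5%, the unpooled formula gives (1.960 + 0.842)² × (0.18×0.82 + 0.38×0.62) / 0.20² = 75.2 per arm. With one look at 65% information and an equal nominal level of about 0.0315 at both looks, the inflation factor is 1.082. Then 75.2 × 1.082 = 81.4, so 82 per arm and 164 in total, as section 13.4 states.

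**Step 1: which drop-outs are converted.** Carry the last weekly status forward over weeks 2 to 6 and look for a run of at least four.

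| Last visit | Run if only that visit was abstinent | Scored a quitter? | Observed abstinent weeks needed |
|---|---|---|---|
| Week 2 | 5 | yes | 1 |
| Week 3 | 4 | yes | 1 |
| Week 4 | 3 | no | 2 |
| Week 5 | 2 | no | 3 |

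If instead the last visit alone decides the outcome, one abstinent visit is enough at any week. If the four-week status reached so far is carried, one abstinent visit is never enough. Under the tolerability rule only drop-outs for other reasons can be converted.

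**Step 2: illustrative size.** Inputs from section 13.4: four-week quit rates of 38% and 18%, and 37% drop-out. Assumptions not in the documents: the window is weeks 3 to 6; a further 20% per arm (range 10% to 30%) are abstinent at week 3 and relapse at week 4, 5 or 6 with equal chance; the last visit of drop-outs is uniform over weeks 2 to 5; nobody is abstinent at week 2.

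Drop-outs as failures:
- DTMS 0.63 × 38 = 23.9%; sham 0.63 × 18 = 11.3%; difference 12.6 points.

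Share of drop-outs scored as quitters by LOCF (last visit at week 2, 3, 4, 5):
- DTMS (0 + 58 + 51.3 + 44.7)/4 = 38.5%.
- Sham (0 + 38 + 31.3 + 24.7)/4 = 23.5%.
- Those converted on one abstinent visit (last seen at week 3): 58/154 = 38% in DTMS and 38/94 = 40% in sham.

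Rates under LOCF:
- DTMS 23.94 + 0.37 × 38.5 = 38.2%; sham 11.34 + 0.37 × 23.5 = 20.0%; difference 18.15 points. A simulation of 400,000 subjects per arm gave 38.3%, 20.0% and 18.3 points.

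**Step 3: where the change comes from.** Split the converted drop-outs into true quitters and relapsers.
- Relapsers (false conversions): 20 × (0 + 1 + 2/3 + 1/3)/4 = 10% of drop-outs in each arm, or 0.37 × 10 = 3.7 points per arm. For 10% to 30% relapsers this is 0.37 × 5 = 1.85 to 0.37 × 15 = 5.55 points.
- True quitters: 0.75 × 38 = 28.5% of DTMS drop-outs and 0.75 × 18 = 13.5% of sham drop-outs. Their effect on the difference is 0.37 × (28.5 − 13.5) = 5.55 points.

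So 12.6 + 5.55 = 18.15. The false conversions raise both rates equally and add nothing to the difference. All of the widening comes from subjects whom the illustration defines as genuine four-week quitters, and the result stays below the assumed true difference of 20 points.

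**Step 4: other conversion shares.** Take 135 per arm with 50 drop-outs. Each 10% of drop-outs converted adds 5/135 = 3.7 points to that arm. Equal shares leave the difference at 12.6. Shares of 30% (DTMS) vs 10% (sham) give 12.6 + 7.4 = 20.0; the reverse gives 12.6 − 7.4 = 5.2. The documents do not say which holds.

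**The case against.** The strongest reply is that little depends on these analyses. They are optional, the governing rule scores drop-outs as non-abstinent, and the list already holds a worst case that is harsher than anything proposed here. Section 13.8.3 adds completer and per-protocol analyses. All of this stands, and it makes the point a minor one.

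A second reply is that the wording does not force the weekly reading. The multiple-imputation bullet speaks of the endpoint as computed at intermediate time-points, so the four-week status reached so far might be what is carried, and an SAP could say so. This is possible but strained. The text carries a visit. With assessments at weeks 2 to 6, no four-week run can finish before week 5, so under that reading LOCF would add almost nothing to the main rule. If it is what is meant, the wording still needs to say so.

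Third, section 13.4 sets aside point prevalence when choosing the planning effect, not for sensitivity analyses, and section 13.2.3 keeps weekly point prevalence as an exploratory endpoint. That stands. The measure is legitimate under its own name; the fault is in presenting it as the four-week CQR.

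Fourth, the size rests on assumed inputs. The illustration places all of the 37% drop-out after a post-baseline visit. The efficacy set in section 13.8.1 leaves out subjects with no post-baseline assessment or too low an average stimulation intensity, so fewer drop-outs may be open to conversion.

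**Conclusion.** The point holds in a limited form. As worded, both rules can score a subject with fewer than four observed abstinent weeks as a four-week quitter, against section 13.2.1 and the main rule. Under week-by-week carry-forward one abstinent visit suffices only when it is the last visit and falls at week 2 or 3; later exits need two or three observed weeks. If the last visit alone decides, one is enough at any week. Under the assumptions above, false conversions add about 3.7 points to each arm's rate (1.85 to 5.55). The primary test, alpha and sample size are not touched.

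A reader might infer that the rules enlarge the treatment difference and so favour the device. The documents do not support this. False conversions cancel between arms when relapse and drop-out are alike, and the widening in the illustration comes from simulated true quitters. With unequal shares the difference could move either way.

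Nor should the movement in the p-value be read as harm. At 135 per arm, z goes from 0.126/0.0464 = 2.72 to 0.1815/0.0553 = 3.28, so p goes from about 0.007 to about 0.001. Both are below the planned 0.03154, and the shift has the same source as the widening.

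**What to change.** In section 13.9.8 (or the SAP), do one of the following for the CQR:

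- count a drop-out as a quitter only with four observed consecutive abstinent weeks, keeping the existing bridging of a missed visit or test; or
- relabel the LOCF and last-valid-assessment results as *abstinent at last visit*, and do not present them as sensitivity analyses of the four-week CQR.

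In their place, run a tipping-point analysis that varies the assumed four-week quit probability of drop-outs separately by arm, between the best-case and worst-case bounds already listed, and report where the conclusion changes. At 37% drop-out those bounds are far apart: with the Step 2 rates the difference runs from 12.6 − 37 = −24.4 to 12.6 + 37 = 49.6 points. The two extremes alone therefore say little, and the grid between them is what informs.

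The cost is a small wording change and one extra analysis on data already collected.

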#### 14.1. Risks

The risks to patients resulting from potential device hazards have been analyzed using the Risk Management Standard - ISO 14971. The different types of hazards were identified and evaluated using risk assessment numerical parameters. Applicable controls for the risks were analyzed. After the implementation of appropriate risk control measures, the level of risk was re-evaluated and found to be acceptable. Most of the identified hazards and risks may be successfully mitigated with appropriate design, manufacturing and appropriate validation methods, such as testing and compliance with international standards and clinical validation in a randomized, double blind, controlled, clinical investigation. Furthermore, instructions manuals and physician training will further mitigate some of the risks.

### 14.2. Benefits

Studies have demonstrated that high-frequency rTMS of the DLPFC can attenuate nicotine consumption (Eichhammer et al., 2003; Amiaz et al., 2009) and craving (Johann et al., 2003). However, the significance and duration of these effects are limited. One possible reason for these partial effects on nicotine consumption might be the superficial magnetic stimulation by the figure-8 coil, which does not reach into the deep layers of the cortex. It is known that nicotine addiction involves various areas of the brain reward system, in which most of them are deeper than the superficial layers of the cortex, like the anterior cingulated, orbitofrontal cortex, nucleus accumbens, and amygdala. Another area of interest which was not stimulated using the superficial rTMS is the insula. The crucial role of the insula in cravings for food, cocaine and cigarettes, was reported by neuroimaging studies (Bonson et al., 2002; Pelchat et al., 2004; Wang et al., 2007). Therefore stimulating the insula and the dipper layers of the lateral PFC could be substantially more effective in treating nicotine addiction. The Brainsway DTMS is designed to stimulate neuronal pathways related to the control of motivation, reward and pleasure, specifically, over the right and left lateral PFC and insula. Previous feasibility studies on a small number of subjects indicated preliminary safety and effectiveness of the treatment as an aid in smoking cessation.

The purpose of this study is to evaluate the efficacy and safety of the DTMS treatments in chronic smokers as an aid in smoking cessation.

# **15. ADVERSE EVENT REPORTING**

Timely, accurate, and complete reporting and analysis of safety information from clinical studies are crucial for the protection of subjects, investigators and the sponsor, and are mandated by regulatory agencies worldwide.

# 15.1. Definitions

15.1.1. Adverse Event Definitions and Classifications

# • Adverse Event

An adverse event is any untoward medical occurrence in a clinical study subject. An adverse event does not necessarily have a causal relationship with the treatment. An adverse event can therefore be any unfavorable and unintended sign (including an abnormal finding), symptom, or disease temporally associated with the use of an investigational product, whether or not related to the investigational product. (Definition per International Conference on Harmonization [ICH])

This includes any occurrence that is new in onset or aggravated in severity or frequency from the baseline condition, or abnormal results of diagnostic procedures, including laboratory test abnormalities.

# • Serious Adverse Event

A serious adverse event as defined by ICH is any untoward medical occurrence that meets any of the following conditions:

- Results in death
- Is life-threatening
- Requires inpatient hospitalization
- Results in persistent or significant disability/incapacity, or
- Is a congenital anomaly/birth defect

Note: Medical and scientific judgment should be exercised in deciding whether expedited reporting is also appropriate in situations other than those listed above. For example, important medical events may not be immediately life threatening or result in death or hospitalization but may jeopardize the subject or may require intervention to prevent one of the outcomes listed in the definition above. Any adverse event is considered a serious adverse event if it is associated with clinical signs or symptoms judged by investigator to have a significant clinical impact.

# • Unlisted (Unexpected) Adverse Event

An unlisted adverse event, the nature or severity of which is not consistent with the applicable product information (e.g. Investigator's Brochure for an unapproved investigational product or the package insert/summary of product characteristics for an approval product) (ICH)

# • Associated With the Use of the Device

An adverse event is considered associated with the use of the TMS if the attribution is possible, probable, or very likely by the definitions listed above.

### 15.1.2. Relationship to Investigational Device

For all adverse events, the relationship to study device and / or procedure will be determined by the investigator, using the following terms:

### • Probably related:

Follows a reasonable temporal sequence from study device delivery / retrieval, and cannot be reasonably explained by known characteristics of the patient's clinical data or the surgical procedure applied.

### • Possibly related:

Follows a reasonable temporal sequence from study device delivery / retrieval but could have been produced by the patient's clinical state or by the surgical procedures regardless of the study device.

#### • Probably not related:

Temporal association is such that the study device is not likely to have had any reasonable association with the observed event.

#### • Not related:

No relationship to study device activation is perceived.

### 15.2. Procedures

#### 15.2.1. All Adverse Events

All adverse events will be reported from the time a signed and dated informed consent form is obtained until completion of the last study-related procedure. Events meeting the definition of serious adverse events must be reported using the Serious Adverse Event Form, including serious adverse events spontaneously reported to the investigator within 30 days after the subject has completed the study (including post study follow up).

All events that meet the definition of a serious adverse event will be reported as serious adverse events, regardless of whether they are protocol-specific assessments. All adverse events, regardless of seriousness, severity, or presumed relationship to study treatment must be recorded using medical terminology in the source document and the CRF. Whenever possible, diagnoses should be given when signs and symptoms are due to a common etiology (e.g., cough, runny nose, sneezing, sore throat, and head congestion should be reported as "Upper respiratory infection"). Investigators must record in the CRF their opinion concerning the relationship of the adverse event to study treatment. All measures required for adverse event management must be recorded in the source document and reported according to sponsor instructions. In the case of a seizure, the investigators will provide to those patients experiencing a seizure a letter documenting that the seizure was experimentally produced. Other potential adverse events which could occur include psychiatric complications (e.g., mania, changes in behavior, hostility, agitation, depression and suicidality), headache, neck pain, intensification of existing headaches, tinnitus, and temporary or permanent hearing loss. The study personnel staff will be responsible for observing the study subjects during the weekly assessments and follow-up visits for such adverse events. In the case of an adverse event, the study investigator will prescribe the appropriate treatment and if appropriate, the subject will be terminated from the study to ensure subject safety.

The sponsor assumes responsibility for appropriate reporting of adverse events to the regulatory authorities. The sponsor will also report to the investigator all serious adverse events that are unlisted and associated with the use of the treatment. The investigator (or sponsor where required) must report these events to the appropriate Independent Ethics Committee/Institutional Review Board (IEC/IRB) that approved the protocol unless otherwise required and documented by the IEC/IRB.

### 15.2.2. Serious Adverse Events

All serious adverse events occurring during clinical studies must be reported to the appropriate sponsor contact person by investigational staff within 24 hours of their knowledge of event.

Information regarding serious adverse events will be transmitted to the sponsor using the Serious Adverse Form, which must be signed by a member of the investigational staff. The initial report of a serious adverse event may be made by facsimile (fax), e-mail or telephone. It is preferable that serious adverse events are reported via fax or e-mail.

Subsequent to a telephone report of a serious adverse event, a Serious Adverse Event Form must be completed by the investigational staff and transmitted to the sponsor within 1 working day.

All serious adverse events that have not resolved by the end of the study, or that have not been resolved upon discontinuation of the subject's participation in the study must be followed until any of the following occurs:

- The event resolves
- The event stabilizes
- The event returns to baseline, if a baseline value is available
- The event can be attributed to agents other that the study treatment or to factors unrelated to study conduct
- When it becomes unlikely any additional information can be obtained (subject or health care practitioner refusal to provide additional information, lost to follow-up after demonstration of due diligence with follow-up efforts)

The cause of death of subject in a clinical study, whether or not the event is expected or associated with the investigational agent, is considered a serious adverse event. Any event requiring hospitalization (or prolongation of hospitalization) that occurs during the course of a subject's participation in a clinical study must be reported as a serious adverse event, except hospitalization for:

- Pre-planned hospitalizations, i.e. before enrollment into the study and which are not related to the disease itself
- Social reasons in absence of an adverse event
- Surgery or procedure planned before entry into the study (must be documented in the CRF)

